The relative hazard of self-reported MVAs during follow-up will be assessed in the final analysis, comparing Lasmiditan Group to Other Acute Medication Group and to No Acute Medication Group, if the required sample size is achieved. Additionally, for self-reported MVAs in the observational period, descriptive statistics will be performed to summarise participants' driving characteristics, severity of the MVA and related injuries, as well as circumstances of the MVA (e.g., migraine status at the time of MVA, use of prescribed anti-migraine medication within 24 hours prior, preceding symptoms, concomitant medication use carrying a risk of MVA, environmental factors) and will be presented per treatment group.

Pharmacy claims records will be reviewed for approximately 60% of enrolled participants (up to 600 participants randomly selected in each treatment group), and the consistency with self-reported anti-migraine medication use will be descriptively reported with relevant agreement statistics, such as percentage of agreement, percentage of disagreement and Kappa statistics. Further details of the planned analyses will be documented in the statistical analysis plan (SAP).

Categorical data will be summarised as frequency counts and percentages (%). Continuous data will be summarised using the mean, standard deviations (SD), median, first and third quartiles (Q1, Q3), minimum, maximum, and the number of non-missing and missing observations.

Missing data will be mitigated by design by requiring answers on all survey questions prior to each participants' submission.

Milestones – Start of data collection (March 2025), interim report submission (March 2026), and final study report submission (December 2027).

5. Amendments and Updates

Not applicable.

6. Milestones

Milestone	Planned date
Registration in the EU PAS register	17 October 2024
Start of data collection	04 March 2025
Interim report submission	31 March 2026
End of data collection	04 September 2026
Final report of study results submission	31 December 2027

Abbreviations: EU = European Union; PAS = post-authorisation study; TBD = to be determined.

7. Rationale and Background

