 - Seriously injured: fractures, concussion, internal injuries, crushings, burns (excluding friction burns), severe cuts, severe general shock requiring medical treatment or death), hospitalisation for the driver.

Circumstances of self-reported MVAs for which the participant was the driver in the last 30 days

- Migraine status at the time and within 24 hours of MVA,
- Use of prescribed anti-migraine medication up to 24 hours prior to the accident (preventive and acute) (medications names, dose and time since medication administration relative to the occurrence of MVA for lasmiditan),
- Symptoms immediately preceding (right before) the accident, including but not limited to aura, headache, fatigue, nausea, dizziness, somnolence, palpitations, vertigo, visual impairment, chest discomfort, muscle weakness, paresthesia, incoordination, lethargy, restlessness and anxiety,
- Use of concomitant medications potentially associated with MVA risk within 24 hours of the accident (including antihistamines, antidepressants, benzodiazepines, beta-blockers, opioids, anti-seizure medications, antipsychotics, sleeping pills including sedatives and hypnotics),
- Influence of alcohol or drugs at the time of the MVA, and
- Time of day, weather, visibility and lighting conditions at time of the accident.

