9.6.2 Missing Data

Data fields in the online survey will be designed to reduce ineligible answers. The online surveys will be configured such that enrolled participants can choose all responses that apply when relevant only. Participants will be required to complete all questions in the online survey, thereby minimising missing data for required items. Where appropriate, questions will include a 'prefer not to answer' option to ensure choice (e.g., racial identity, level of education). Select items may not be applicable to all participants and will be recorded appropriately in the study platform.

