9.6.4 Study Compliance and Lost to Follow-up Participants

Virtual site staff will monitor whether participants are completing the online surveys. Participants who do not complete the study steps (e.g., the baseline online survey, the follow-up online surveys) will be contacted by phone call and/or text message with reminders to complete tasks within a time window that is appropriate to the specific task; participants will remain in the study sample regardless of whether they submit data in a timely manner.

Participants who begin the enrolment registration process will remain active and able to complete their enrolment until recruitment targets are reached, at which point they will be notified the study is no longer actively recruiting.

For follow-up online surveys sent every 30 days after the baseline survey, participants will be sent an automated reminder to complete their online survey, which be available for completion for 1 week. Additional automated reminders will be sent as needed, and study staff will contact the participant via phone 1-2 days before the survey window expires to address any barriers to completing the survey. After 1 week passes, access to that follow-up online survey will close. An invitation for the subsequent follow-up survey will be sent according to the schedule determined at baseline.

If a participant does not respond to two consecutive online survey invitations, IQVIA will make no more than five additional attempts, including outbound calls and other means of communication as appropriate, to contact the participant and encouraging to respond to the most recent survey invitation, and/or the alternative contact provided at enrolment. If there is no response to the fifth attempt, the participants will be considered lost to follow-up. All available information in the participants' file through the date of last contact or survey completion will be recorded for the lost to follow-up participants. The statistical analysis plan (SAP) will specify how such participants will be considered for purposes of endpoint assessment.

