9.9.2 Information Bias

As with all collection of self-reported data, there is the possibility that participants may give inaccurate responses. For prescription anti-migraine medication, agreement between self-report and pharmaceutical claims data was notably higher when participants were asked to report 'current' use (kappa statistic 0.66, 95% confidence interval [CI] 0.23-1.00) relative to the results for a recall period of the past year (kappa statistic 0.36, 95% confidence interval [CI] 0.00-0.72). (Lacasse et al. 2016) Validation with pharmacy claims data will assess the internal data validity of self-reported prescription medication.

Sensitive data regarding MVAs are being collected in the study, including whether the accident was reported, the use of medications, drugs, or alcohol prior to the accident, and/or distracted driving, which could predispose participants to not answer truthfully due to the fear of judgment or embarrassment. For MVAs, there is evidence that self-reported data has poor test re-test reliability. (af Wåhlberg and Dorn 2015) The risk of social desirability bias may be mitigated by use of an anonymised online survey, combined with assurance on data privacy, compared to interview-based methods. This will be emphasised in the survey instructions to encourage accurate and truthful responses from participants. Moreover, participants will not be able to change answers once they are submitted and will not be contacted to clarify or revise responses at any point. If a participant reports illegal activities (i.e., taking illegal drugs or taking medications that are not allowed before driving), he will be aware that no action will be taken.

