9.9.5 Missing Data and/or Dropout

Missing items will not be permitted by the online survey and so intermittent missingness is not expected. Anticipated missing data could be due to participants exiting the questionnaire before completion and as for any longitudinal study, attrition and loss-to-follow-up may occur. However, participants may not complete all surveys included as part of the study design (e.g., every 30 days for 12 months).

It could also happen that a participant has a very serious/severe accident and due to injuries or death, information will not be known/reported for the study, which could lead to underestimation of MVA incidence. This will be mitigated by requiring participants to designate an alternative contact who can confirm information if the participant is unable to be reached (see Section 9.3.5 for details of what may be requested from the alternative contact) Missing data arising from non-response will be addressed using *last observation carried forward*, (See Section 9.7.2.2.2.3).

10. Protection of Human Subjects

This study will be submitted to at least one ethical review board (ERB) for review and to confirm that the study is considered non-interventional. Regulatory authorities will be notified and approval sought as required by local laws and regulations. This observational study will be performed in accordance with ethical principles that are consistent with the Declaration of Helsinki (WMA 2013), the ICH guideline E6R1 (International Council for Harmonisation 1996) and the Good Pharmacoepidemiology Practices (GPP) issued by the International Society for Pharmacoepidemiology (ISP 2015) and the applicable legislation on non-interventional studies and/or observational studies.

11. Management and Reporting of Adverse Events/Adverse Reactions

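### Full-completion submission leaves the MVA answer unsecured: a minor accident entered in a survey that is not finished may go uncounted while its person-time is kept

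*Protocol*

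**What the plan says.** The Abstract (Section 4, Data Analysis) presents compulsory completion as a safeguard: "Missing data will be mitigated by design by requiring answers on all survey questions prior to each" participant's submission. Section 9.6.2 repeats it: "Participants will be required to complete all questions in the online survey, thereby minimising missing data for required items". Section 9.8 states the same requirement under quality control.

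Section 9.9.5 still foresees abandonment: "Anticipated missing data could be due to participants exiting the questionnaire before completion". Section 9.9.2 describes the accident items as sensitive in a way "which could predispose participants to not answer truthfully due to the fear of judgment or embarrassment".

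Section 9.3.4 lists what a driver with an MVA is asked beyond its number and date: location, damage, speed, other parties, fault, injuries, migraine status, medication in the previous 24 hours, symptoms, alcohol or drugs, and conditions. For lasmiditan taken in those 24 hours it adds "dose and time since medication administration relative to the occurrence of MVA for lasmiditan". Section 9.4.2 says the survey uses logic to shorten the time spent by participants.

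On timing, Section 9.6.4 says: "After 1 week passes, access to that follow-up online survey will close". An opt-out exists in Section 9.6.2: "Where appropriate, questions will include a 'prefer not to answer' option to ensure choice (e.g., racial identity, level of education").

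**The concern.** The first MVA as driver is the primary outcome, and the submission rule ties it to completion of a long set of further questions that only drivers with an MVA have to answer. A participant without an MVA has no such module. Failure to submit can therefore depend on the outcome itself.

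Two results are exposed. The crude incidence rates, which become the primary analysis if the sample is too small (Sections 9.5 and 9.7.2.2) and feed the benchmark comparison (Section 9.7.3), would be too low. The comparative analysis would lose events, and with roughly 71 expected in a two-group comparison there are few to spare.

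The censoring weights in Section 9.7.2.2.2.2 do not help. A single skipped survey is not a censoring event, and an MVA that was never recorded appears in no covariate.

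**Working it through.** **Step 1: can an MVA in an unsubmitted survey be recovered?**

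- Submission needs every question answered (Abstract, 9.6.2, 9.8).
- The survey closes after 7 days (9.6.4).
- The next survey asks about MVAs in the past 30 days (9.3.4), so it is not designed to pick up one from the interval before.
- The alternative contact may be approached only after two consecutive non-responses, and is asked about death and MVA-related hospitalisation or serious injury (9.3.5). A minor MVA has no such route.
- One missed survey is a skip; loss to follow-up needs two in a row (9.2.4.4, 9.7.2.2.2.3). For a skip, treatment and confounders are carried forward (9.7.2.2.2.3).
- The event indicator is 1 if the event occurred in the next interval and 0 otherwise (9.7.2.2.2.1). With nothing recorded, the interval counts as event-free follow-up.

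A special case is the first interval. The primary population must have completed the first follow-up survey (9.7.2.2.1), so a participant who leaves that survey unfinished because of an MVA does not meet the population definition.

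No section says whether entries in an unsubmitted survey are kept.

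**Step 2: reproduce the planned sample size.** Inputs from Section 9.5: comparator risk 3%, HR 2.0, 80% power, 5% level (two-sided assumed).

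- Lasmiditan risk: 1 − 0.97² = 0.0591.
- Freedman events: (1.96 + 0.8416)² × [(2 + 1)/(2 − 1)]² = 70.64.
- Per group: 70.64 / (0.03 + 0.0591) = 792.8, i.e. 793, as stated. With 20% dropout: 793 / 0.8 = 991.25, i.e. 992, as stated.
- Expected events at 793 per group: 46.9 + 23.8 = 70.7.

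**Step 3: effect of lost MVAs.** The loss fractions are assumptions; the documents give none. Each group's risk is multiplied by (1 − loss). The observed HR is ln(1 − risk, lasmiditan) / ln(1 − risk, comparator). Power is Φ[√events × (HR − 1)/(HR + 1) − 1.96].

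| Loss, lasmiditan | Loss, comparator | Events | Observed HR | Power |
|---|---|---|---|---|
| 0% | 0% | 70.7 | 2.00 | 80% |
| 5% | 5% | 67.1 | 2.00 | 78% |
| 10% | 10% | 63.6 | 2.00 | 76% |
| 20% | 20% | 56.5 | 1.99 | 70% |
| 30% | 30% | 49.5 | 1.99 | 64% |
| 20% | 10% | 58.9 | 1.77 | 57% |

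Worked line for 20% versus 10%: risks 0.0591 × 0.8 = 0.0473 and 0.03 × 0.9 = 0.027; HR = ln(0.9527)/ln(0.973) = 1.77; events = 793 × 0.0743 = 58.9.

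Equal loss of 10% or 20% turns a true comparator risk of 3.0% into 2.7% or 2.4%.

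**The case against.** The strongest reply is that the loss is inferred. No passage says that partial entries are discarded. Section 9.6.4 records all available information for participants lost to follow-up and leaves their endpoint handling to the SAP. The survey instrument, its question order and the data management plan are not shown. This stands against any claim that such an MVA is certain to be lost. It does not close the gap: the deferral covers participants lost to follow-up, not a single skipped survey, and a SAP cannot recover an answer that the platform did not store.

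The protocol also works to secure completion. Participants are paid per survey (9.2.4.4), reminders are sent, and "study staff will contact the participant via phone 1-2 days before the survey window expires to address any barriers to completing the survey" (9.6.4). Cognitive interviews test the items, privacy is assured, and the opt-out answer may extend beyond its two demographic examples. These measures should lower abandonment; none of them records the MVA answer by itself.

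A reader might infer two stronger things. One is that a driver who abandons one survey is lost as a non-responder. The documents say otherwise: one missed survey is a skip and the participant stays. The other is that the rule hides a lasmiditan signal because lasmiditan users face extra questions. The dose and timing items apply only when lasmiditan was used in the 24 hours before the accident, whereas one use in 30 days places a participant in the Lasmiditan Group (Section 9.1). Other drivers with an MVA also face items on alcohol, opioids and fault. Section 9.9.2 anticipates untruthful answers, not abandonment. Unequal loss is plausible but nothing in the documents shows it.

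Finally, an unsubmitted yes may be an entry error. That is a fair limit on the remedy and is met below.

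**Conclusion.** The point holds as a gap in data capture. The protocol forces complete submission, expects early exits, and has no rule that keeps the MVA answer when the rest of the survey is unfinished. A minor MVA in such a survey may go uncounted while its interval remains as event-free person-time.

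The size cannot be fixed from the documents. Under assumed equal loss of 10% to 20% of MVAs, incidence falls by the same share and power drops from 80% to 76% and 70%, with the HR practically unchanged. Bias of the HR towards 1 needs greater loss with lasmiditan; the 20% versus 10% case (HR 1.77, power 57%) illustrates this and is not a prediction. The calculation uses the protocol's 793 per group, 3% risk and HR 2.0, with no confounding.

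The protocol should be changed here, because the remedy is cheap and has to be in place at data collection.

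**What to change.** Amend Sections 9.6.2, 9.8 and 9.7.2.2.2.3, and align the Abstract:

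1. Put MVA as driver (yes/no), number and date(s) on a separate screen near the start of each survey, with a confirmation step. Store it on entry. Count a confirmed yes as the outcome even if the rest is not submitted, and add a sensitivity analysis restricted to submitted surveys.
2. Offer 'do not know' and 'prefer not to answer' on every MVA-circumstance item.
3. Report by treatment group how many surveys were opened but not submitted, and how many of these held an MVA yes.

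The cost is platform configuration and a few sentences in the protocol and SAP. Some circumstance items that are now compulsory will be missing, which affects the descriptive secondary objective. A few unsubmitted yes entries may be errors; the confirmation step and the sensitivity analysis limit and expose these.

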9.1 Study Design

This is an observational cohort study, aiming to compare the one-year risk of MVA associated with three treatment strategies of interest, in patients with migraine in the US. The comparative treatment strategies of interest, as well as other core elements of the study design, are described in Table 1. No visits, examinations, laboratory tests, or procedures are mandated or recommended as part of this study.

Eligibility Criteria	 Participant age is 18 to 74 years old at enrolment; Participant has a valid driver's licence that they received ≥1 year before enrolment; Participant has access to a vehicle at the time of enrolment and anticipates having access to a vehicle for the next 12 months (at enrolment); Participant must confirm having driven at least once during the 6 months prior to enrolment; Participant must provide informed consent to participate in this study; Participant must be able to read and understand English; Participant must currently reside in the US; Participant must have access to a personal device with internet connection; Willing to complete study surveys once every 30 days for 12 months at enrolment; and Participant must be willing to provide consent to access their antimigraine medication prescription claims data from ExamOne ScriptCheck and allow HCP to confirm migraine diagnosis, completing the Health Insurance Portability and Accountability Act of 1996 (HIPAA) Authorisation/Medical release Form.
Treatment strategies	 Use of lasmiditan exclusively or in conjunction with other acute antimigraine migraine medication for up to one year; Use of any non-lasmiditan prescribed acute anti-migraine medication (see medications list in Annex 3) for up to one year; and No use of any prescribed acute anti-migraine medication for up to one year. Self-reported use of prescribed acute anti-migraine medications will be utilised to assign treatment exposure category. The self-reported use of prescribed preventive anti-migraine medication will not be considered for treatment group classification

Table 1.Core Study Elements for The Primary Analysis using a 'Nested Trial'
Approach

Outcome	Self-reported first occurrence of MVA for which the participant was the driver since study enrolment.
Follow-up	 Start: Date(s)^a participant meets all eligibility criteria (baseline survey) End: Earliest of the following events: Outcome event, Loss to follow-up (e.g., non-response of two consecutive surveys)^b, Participant withdrawal, Deviation from assigned treatment strategy (e.g., treatment change), Loss of eligibility, and Administrative end of study (one-year of follow-up).

Abbreviations: HCP = Healthcare Practitioner; HIPAA = Health Insurance Portability and Accountability Act; MVA = motor vehicle accident

^a Participants may meet eligibility criteria at numerous calendar dates. The study design permits participants to enter the analytic cohort repeatedly (i.e., at each calendar date that participant is study-eligible) during the participant enrolment period (see Section 9.1 for a detailed description).

^b Participants who are lost to follow-up will be censored at 67 days following the opening of their last survey (as participants are allotted 7 days to answer each monthly survey).

Data on potential confounders, treatments received, and occurrence of the outcome event over follow-up will be ascertained with a series of monthly surveys administered sequentially over the 12 months following enrolment (see Section 9.3.4). The initial (baseline) survey will collect additional information on potential confounders and treatments in the year prior to enrolment (see Section 9.3.3). To align with the primary research objective, only the first occurrence of MVA since study enrolment will serve as the outcome of interest for primary analysis.

Given that patients may be eligible for study entry at multiple calendar times, and that their eligibility may fluctuate over the course of the study (e.g., due to loss of access to a vehicle or driving privilege for one or more months), a 'nested trial' approach will be implemented (Danaei et al. 2013; Danaei et al. 2018). In this approach, the raw survey data collected from participants will be transformed into an analytic dataset as follows:

- 1. Select participants who are study-eligible on the first calendar day of study recruitment and assign their analytic 'time zero' to this day.
- 2. Assign each participant to one of the three treatment strategies of interest (see Table 1) based on their self-reported use of prescribed anti-migraine medications in the prior 30 days: participants who used lasmiditan at least once (Lasmiditan Group), participants who used another prescribed acute anti-migraine medication (includes, but is not limited to, triptans, ubrogepant [Ubrelvy], rimegepant [Nurtec], zavegepant [Zavzpret]; see Annex 3 for the complete list) at least once and did not use lasmiditan (Other Acute Medications Group), and participants who did not use any prescribed acute anti-migraine medication

(No Acute Medication Group). The self-reported use of prescribed preventive antimigraine medication will not be considered for treatment group classification.

- 3. Collect and record each participant's self-reported and calculated confounder history prior to their analytic 'time zero' (see Section 9.7 for potential confounders of interest).
- 4. Define follow-up for each participant from analytic 'time zero' until the earliest of the following: outcome event, loss to follow-up (day 67 of non-response, corresponding to non-response on two consecutive surveys), participant withdrawal, deviation from assigned treatment strategy (e.g., treatment switch), loss of eligibility, or administrative end of study (one-year of follow-up).
- 5. Generate a counting-process formatted dataset for this 'nested trial' derived from longitudinal treatment, outcome, and confounder information assessed in Steps 1-4 (see Section 9.7.2.2.2.1 for example data structure).
- 6. Repeat Steps 1-5 above for each sequential calendar day in which participants will be recruited into the survey study.
- 7. Bind all datasets produced in Step 5 by row. This will serve as the analytic dataset for the primary analysis (see Section 9.7.2.2.2.1 for example data structure).

The 'nested trial' approach has several distinctive advantages. First, it permits greater statistical power by leveraging information following treatment changes in participants over follow-up. For example, if a participant switches treatment strategy from lasmiditan to other prescribed acute antimigraine medication, that participant will contribute person-time to two separate 'trials' (each associated with a single treatment strategy), provided they remain study-eligible. Second, the approach allows the investigator to specify precise and dynamic treatment strategies of interest for comparison, while accounting for potential confounders that have changed since baseline enrolment in the survey study. Third, seasonality of MVA can be accounted for as data within each 'nested trial' is aggregated by calendar time. Fourth, time-varying and time-dependent factors can be accounted for easily with the data structure generated by this approach, including dynamic study eligibility and evolving confounder histories.

Self-reported survey data on prescription migraine medication use (acute and preventive) will be compared with pharmacy data (including prescribed drug and dosage), obtained via linkage with ExamOne ScriptCheck (additional information in Section 9.4.3) to describe concordance.

Participants for this study will be recruited through healthcare practitioner (HCP) referrals. This study will utilise IQVIA Primary Intelligence Research Service (PIRS) to identify and recruit HCPs providing care to the population of interest into a network of referring providers. The HCPs who opt into the study will be able to refer potentially eligible and interested participants with migraine.

The study comprises 2 phases: Phase 1 includes development activities for surveys planned to be administered during Phase 2; while Phase 2 includes prospective follow-up of study participants as well as validation of self-reported prescription medication data for a subset of participants in each treatment group. The study will be administered by one central virtual site managed by IQVIA and a central principal investigator (PI). Using a central PI delivery model is designed to leverage

one PI to provide oversight on the participants' rights, safety, and welfare, and ensure data quality and integrity. Additional details are described below.

Interested and potentially eligible participants will be provided a link to enrol in the study by their HCP. Screening will be conducted for both phases of the study. For Phase 1, patients will follow the link to an online Institutional Review Board- (IRB-) approved screener programmed through Confirmit to complete screening and enrol in the study. For Phase 2, all patients are sent into the IQVIA Health Research Space (HRS) study platform to enrol and upon successful screening, participants will continue through to the baseline survey. Both the link to the online screener platform (Phase 1) and IQVIA HRS study platform (Phase 2) can be accessed on personal devices with internet connection such as phone, tablet or computer via secure web-link. During the screening, the participants will be asked to confirm their eligibility based on the eligibility criteria outlined in Sections 9.2.1 and 9.2.2. After confirming eligibility via screening, participants will provide informed consent for the study via an online consent form (Phase 1) or directly in the HRS study platform (Phase 2).

